## **18.0 Provisions to Monitor the Data to Ensure the Safety of Participants**

### *18.1 Data Integrity Monitoring.*

This trial will be conducted in compliance with this protocol, good clinical practice, and the applicable regulatory requirements.

Study Oversight. Continuous study oversight will be provided by the study's PI, [name], Vice Chair of Research, Department of Rehabilitation Medicine, University of Minnesota ([[contact]](mailto:[contact]), [contact]), Co-I, [name], Swedish Medical Center, and Co-I/study physician, [name], University of Miami collaborator.

Plan for Data Management. Data will be collected electronically (imaging files) or on paper forms. All electronic data will be stored on Box Secure Storage or REDCap. Paper forms will only be accessible by the study staff, trained study coordinator, and the principal investigator. All these documents will be kept in locked file cabinets in locked offices at all times. Participant names, contact information, health history, and other information that can be traced back to the participant will be kept separately from data collected for the study. Protocol sheets used during data collection will only have the participant's ID.

MRI imaging data will be identified by study ID without personal identifiers and stored on the system drive behind the institutional firewall. All computers are password-protected and will only be used by trained study staff and for study purposes only.

All study records will be kept indefinitely after the study is closed. Research records will be stored in a manner to protect the confidentiality of participant information.

#### 18.2 Data Safety Monitoring

Plan for Monitoring Safety. The safety environment of UMN participants will be overseen and monitored by PI, [name], Co-I, [name], and Co-I/study physician, [name]. We will monitor to assure that participants meet eligibility criteria; that the informed consent process is conducted appropriately, that the data will be collected and analyzed as specified in the protocol, that adverse events (defined below) are reviewed promptly and reported as required (detailed below), that dropouts are documented, and that primary and secondary endpoints are evaluated. According to the data safety-monitoring plan, study participation will be terminated immediately in the event of injury or increased morbidity (drug intolerance). Data and all procedures will be monitored at each measurement time point and monthly throughout the duration of the study to ensure the safety of participants.

We will establish a Data Safety and Monitoring Board (DSMB) in accordance with NIDILRR and FDA guidance for clinical trial sponsors. UMN's institutional CTSI will assist with identifying board members and assist with managing board activities. The DSMB will review safety and efficacy data following a recruitment pause after the first 20 participants are enrolled and will make recommendations regarding continuation or termination of the study. The DSMB will also meet and review safety data quarterly and as needed throughout the duration of the study. The safety environment of all participants will be overseen and monitored by [name] (study Co-I). We will monitor to assure that participants meet eligibility criteria; that the informed consent process is conducted appropriately, that the data will be collected and analyzed as specified in the protocol, that adverse events are reviewed promptly and reported as required, that dropouts are documented, and that primary and secondary endpoints are evaluated. Data and all procedures will be monitored at each measurement time point and monthly throughout the duration of the study to ensure the safety of participants.

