**Table 1. Study Procedures**

Study Task	Screening	Visit 1 b	Visit 2 b	7-week intervention	Visit 3 c (end of study testing)	Visit 4 c
Screening Phone Survey	X					
Consent/randomization		X				
MRI Brain Scan (optional)			X		X	
Blood draw for biomarkers (optional)			X		X	
Physical health exam, health history screening		X			X	
Surveys		X			X	X c
Dispense study drug			X			
7-week drug intervention				X		
Limited safety labs (blood draw, required)	X a				X	
Pregnancy test (for women of child-bearing potential)					X	
Drug dose reduction protocol					X c	
Participant return remaining pills, bottle, and medication diary via mail					X c	
Adverse Events, PHQ-9, pain rating (highest, lowest, average)				Assessed weekly c		

PHQ-9: Patient Health Questionnaire 9-item

aMedical clearance must be clinically obtained from participants' primary care provider or other healthcare provider within 1 month prior to visit 1

bVisits 1 and 2 may be combined for participant convenience

cPerformed at the time of early withdrawal for those not completing the study

**Study drop criteria:** Participants will be removed from the study for safety reasons including drug intolerance, drug allergy, drug contraindications, development of depression, aggressive behavior, anxiety, or suicidality, or evidence of brivaracetam adverse events according to the manufacturer's prescribing guide (package insert). Poor drug compliance will be recorded for consideration during the analysis but will not be cause for removal from this study. In the case of drug intolerance, participants will reduce the drug dose under medical supervision of the PI until the drug can be safely discontinued.

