## **12.0 Withdrawal of Participants**

Withdrawal Circumstances:

At any time after enrollment, a participant may be discontinued. Reasons for discontinuation of a participant from the study will include, but may not be limited to, the following:

- The participant is found to be intolerant to a required study procedure at any time point
- Failure of the participant to adhere to protocol requirements
- Positive hGC for individuals of childbearing potential
- The participant experiences a serious adverse experience at any time point
- The participant develops an inter-current illness that would, in the judgment of the investigator, affect assessments of clinical status to a significant degree.
- The participant enrolls in another investigational study
- The participant requests to withdraw from the study

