**Termination Procedures:**

Participation may be terminated due to drug intolerance or allergy and based on clinical judgement of the study team. All data collected will be retained and analyzed unless the participant specifically requests to have their data withdrawn from the analysis.

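### For participants removed for drug intolerance, the Visit 3 pain rating moves to the withdrawal date; nothing keeps the scheduled rating or says which one is primary

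*Combined protocol and SAP*

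**What the plan says.** Three places deal with drug intolerance, and they differ in force.

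- Section 18.2, Data Safety Monitoring: "study participation will be terminated immediately in the event of injury or increased morbidity (drug intolerance".
- Section 5.0, study drop criteria (below Table 1): "Participants will be removed from the study for safety reasons including drug intolerance, drug allergy, drug contraindications". The same paragraph has the dose brought down under supervision until the drug can be stopped.
- Section 12.0, Termination Procedures: "Participation may be terminated due to drug intolerance or allergy and based on clinical judgement of the study team".

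Section 4.0 offers a partial way to stay in. Participants may lower the dose for unacceptable side effects, which it defines as increased somnolence, but they must hold at least 50 mg BID to complete.

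On data, footnote c of Table 1 is attached to the Visit 3 and Visit 4 columns and reads "Performed at the time of early withdrawal for those not completing the study". It is also on the weekly row, "Adverse Events, PHQ-9, pain rating (highest, lowest, average". Section 12.0 adds: "All data collected will be retained and analyzed unless the participant specifically requests to have their data withdrawn from the analysis".

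Section 15.1 makes the main analysis Intention-to-Treat. It does not say which rating represents a participant who left early.

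**The concern.** An Intention-to-Treat comparison needs the outcome at the planned time for everyone randomised, on or off drug. Here a drug side effect ends study participation, and with it the planned rating. What remains is a rating at withdrawal. Because the primary instrument asks about average pain over the last week (Section 5.0), that rating describes the ramp-up or a partial course, not the end of treatment. If the withdrawal assessment is missed, there is no Visit 3 value at all.

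The reason for the early value is plausibly related to treatment. Sections 4.0 and 13.0 name somnolence as an expected effect of the drug, so early or missing ratings may fall more on the active arm. Two analysts could then treat the same early rating differently, one using it as the primary value and one setting it aside, and both could say that they had followed the plan.

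**Working it through.** **1. Does intolerance end dosing or participation?** Sections 5.0 and 18.2 both end participation, with *will*. Section 12.0 says *may* and leaves it to clinical judgement. Section 4.0 retains some participants with somnolence at a reduced dose. So removal is the stated rule in two places, but it is not certain for every participant with side effects.

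**2. Where does the pain rating go?** Footnote c moves the Visit 3 assessments to the withdrawal date. Section 12.0 keeps what has already been collected. The weekly calls and the daily diary (Section 5.0) add earlier pain data. None of these provides the rating on the primary instrument at the scheduled Visit 3 after removal.

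**3. How early would the rating be?** Section 4.0 gives 1 week at 50 mg BID plus 28 days at 100 mg BID, so 1 + 4 = 5 weeks. Visit 3 in Section 5.0 is 5 weeks after Visit 2. The 2-week taper follows Visit 3, and 5 + 2 = 7 accounts for the 7-week course. Table 1 and the imaging paragraph of Section 5.0 can instead be read as placing Visit 3 after the full 7 weeks. The gap is the scheduled week minus the week of removal; the removal weeks below are examples.

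| Removal at | 5-week schedule | 7-week reading |
|---|---|---|
| Week 1 | 5 − 1 = 4 weeks early | 7 − 1 = 6 weeks early |
| Week 3 | 5 − 3 = 2 weeks early | 7 − 3 = 4 weeks early |

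The dosing schedule favours the 5-week column. The extensions allowed in Section 4.0 would lengthen the gaps if Visit 3 moved with them.

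**4. Visit 4.** Section 5.0 sets it 1 month after the end of study drug. If footnote c is read literally, it is done at withdrawal, before the taper has ended. Assuming the Section 4.0 taper applies (1 week from 50 mg BID, 2 weeks from 100 mg BID) and 1 month is about 4 weeks, that is 1 + 4 = 5 to 2 + 4 = 6 weeks ahead of its definition. This depends on the literal reading.

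**5. How many participants?** Section 10.0 plans 48 enrolled and 40 completing: 48 − 40 = 8, and 8/48 = 16.7%. The stated 20% would be 0.20 × 48 = 9.6. These are losses from all causes in both arms, and the share due to intolerance is not given.

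**6. Can the bias be sized?** No. The documents give no intolerance rate and no ratings after stopping. As an illustration only, assume that no one on placebo is removed, that the benefit is 2 points (the Section 15.2 target) for those who stay on active drug, and that it is zero at the scheduled Visit 3 for a share *w* of the active arm who stop. The effect in all randomised is 2 × (1 − *w*):

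| *w* | All randomised | Completers only |
|---|---|---|
| 5% | 1.9 | 2.0 |
| 10% | 1.8 | 2.0 |
| 20% | 1.6 | 2.0 |
| 30% | 1.4 | 2.0 |

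This shows why the choice of rating matters. It does not describe an analysis that uses the early rating, which could err either way: taken on drug, it might credit relief that would not last to Visit 3, or it might precede an improvement that would have come by then.

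**The case against.** The strongest reply is that the plan already has a safeguard. Footnote c secures an assessment at withdrawal, Section 12.0 retains and analyses it, dose reduction keeps some participants in, and Section 12.0 leaves termination to judgement. That stands. A reader might infer that no endpoint is collected after intolerance, or that every participant with side effects is removed; neither follows. What remains is that the rating is early and its role in the analysis is not stated.

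A reader might also infer from the 20 per arm in Section 15.2, which equals the 40 expected completers, that non-completers are left out of the primary comparison. The documents do not support that. Enrolling 48 to finish with 40 is an ordinary allowance for attrition, and Section 15.1 states Intention-to-Treat.

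It can be said that safety requires removal. Safety requires stopping the drug, and nothing here should delay that. In particular, it would be wrong to read Section 4.0 as a general rule to try 50 mg BID before stopping: it allows reduction for somnolence, and Section 18.2 acts at once.

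Finally, using an off-drug rating at Visit 3 is a choice of estimand. That is so, but it is the choice that best fits the Intention-to-Treat analysis already stated. Section 5.0 also already accepts following people who are not taking the drug as directed: "Poor drug compliance will be recorded for consideration during the analysis but will not be cause for removal from this study". Section 12.0, however, lists "Failure of the participant to adhere to protocol requirements" as a possible reason for discontinuation. That this is a pilot limits the consequences; it does not make the early rating equivalent to the planned one.

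**Conclusion.** The point holds as a gap in follow-up and in the definition of the primary value, not as a demonstrated bias. Followed as written, the plan would give the Intention-to-Treat analysis an early primary rating, or none if the withdrawal assessment is missed, for some participants whose reason for leaving is plausibly related to treatment. On the 5-week schedule the rating would be about 4 weeks early for removal at week 1 and about 2 weeks early for removal at week 3. The longer gaps depend on the 7-week reading, and the Visit 4 consequence on a literal reading of footnote c.

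That intolerance is commoner on active drug is an assumption. The number affected is an unknown part of 8 of 48, and the size and direction of any bias cannot be computed. The change is worth making because it is cheap and removes a foreseeable ambiguity in the primary outcome.

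**What to change.** Leave every trigger for stopping or tapering study drug exactly as it is. Then:

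1. In the Section 5.0 drop criteria, Section 12.0 (Termination Procedures) and Section 18.2, state that these triggers end study drug and do not end follow-up.
2. Amend footnote c of Table 1 so that, in addition to the assessment at withdrawal, the Visit 3 and Visit 4 pain and adverse-event assessments are kept at their scheduled times for all randomised participants, remotely if needed, unless consent is withdrawn.
3. In Section 15.1, state that the Intention-to-Treat analysis takes the scheduled Visit 3 rating, not the early-withdrawal rating, as the primary value.

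The cost is wording in four sections and one footnote, a few extra contacts with participants who are off drug, and possibly a consent wording update with IRB review. The visits already exist, and Section 5.0 already allows fully remote participation.

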Assessment of Risk. This is a moderate risk pilot clinical study. As such, our safety monitoring plan will include a medical monitor: [name]. Drs. [name] and [name] will review all reported adverse events on a monthly basis with [name], the medical monitor. Additionally, Drs. [name] and [name] will inform [name] immediately of all study-related unanticipated problems involving risk to volunteers or others, serious adverse events, and all volunteer deaths associated with the protocol, and provide an unbiased written report of the event to the IRB. The medical monitor will comment on the outcomes of the event or problem, and in the case of a serious adverse event or death, comment on the relationship to participation in the study. The medical monitor will also indicate whether he concurs with the details of the report provided by the study investigator. Reports for events determined by either the investigator or medical monitor to be possibly or definitely related to participation, and reports of events resulting in death will be promptly forwarded to the IRB.

## **19.0 Provisions to Protect the Privacy Interests of Participants**

### **Protecting Privacy:**

Study staff will receive HIPAA and data security training to maintain participant confidentiality prior to the initiation of participant recruitment. Non-identifiable research related data will be directly entered by participants into REDCap. REDCap is a secure, web-based application designed to support data capture for research studies. Trained staff will double enter data from de-identified case report forms containing variables collected on questionnaires. All paper form files with personal identifiable information will be stored in locked filing cabinets. Electronic files containing personal identifiers will be stored on Box Secure Storage and REDCap. In the instance that participants engage in a study-related videoconference through the Zoom video-conferencing platform, Zoom does not have access to identifiable protected health information, and they protect and encrypt all audio, video, and screen-sharing data. Zoom sessions will not be recorded or maintained. All study staff will receive training on privacy standards for maintaining participant confidentiality. The informed consent form and the HIPAA form will be signed with eSignature using a REDCap form that is compliant with FDA Title 21 CFR Part 11. For more information on REDCap compliance, please visit: [https://redcap.ahc.umn.edu/surveys/?s=3PT9FY73NC&topics\\_\\_\\_ec=1#ec](https://redcap.ahc.umn.edu/surveys/?s=3PT9FY73NC&topics___ec=1#ec)

Procedures are in place for maintaining the full confidentiality of all information collected. Participant confidentiality will be protected by securing all hard copy study files in locked filing cabinets. Electronic files containing personal identifiers will be stored on Box Secure Storage or REDCap. All study staff receive training on privacy standards for maintaining participant confidentiality. All published reports will be of summary nature and no individual participants will be identified beyond the investigative staff involved in the project.

### **Access to Participants:**

Participants have been fully informed of the ways in which their data will/may be used during the informed consent process. The research team has been trained in conducting these conversations and the participants are also assessed for their understanding of consent prior to signing the consent form or initiating any study procedures.

## **20.0 Compensation for Research-Related Injury**

Compensation for Research-Related Injury:

In the unlikely event that a participant is injured as a result of this research study, medical care, including emergency treatment will be provided. The participant's insurance company may be billed for treatment.

Contract Language: N/A

## **21.0 Consent Process**

### **21.1 Consent Process (when consent will be obtained):**

Informed consent will be obtained by study staff electronically via REDCap, in person at the enrolling site, or a location convenient to the participant by study. For participants who meet the inclusion criteria, a qualified member of the study team will follow the informed consent process over Zoom, and the participant will provide consent through the REDCap eConsent form. Prior to obtaining consent, all participants will be given ample time to read the consent form and encouraged to ask questions. Potential participants will be reminded that participation is strictly voluntary and will not affect their current or future care at the enrolling site or any affiliated institute. Each participant will be told that they will be free to discontinue participation at any time, but that discontinuation of the drug must be done under medical supervision to ensure it is done safely. A copy of the signed informed consent form will be sent or given to the participant. Participants will be provided with [name] contact information if questions should arise during the course of the trial. Consent will be obtained only from the participant and we will not seek consent from legally authorized representatives. We will not enroll any participants unable to give consent due to altered mental capacity. We will not enroll children therefore will not obtain assent.

### **21.2 Waiver or Alteration of Consent Process (when consent will not be obtained): N/A**

### **21.3 Waiver of Written/Signed Documentation of Consent (when written/signed consent will not be obtained): N/A**

### **21.4 Non-English speaking Participants:**

We will include enrollment of non-English speaking participants. We will provide a translator to interpret consent forms. The interpreters are trained and required to protect participant privacy. Additionally, PI [name] will also be available as needed to carry out study procedures in Spanish, correspond with Spanish-speaking participants, and provide Spanish-English translation.

21.5 Participants Who Are Not Yet Adults (infants, children, teenagers under 18 years of age): N/A

21.6 Cognitively Impaired Adults, or adults with fluctuating or diminished capacity to consent: N/A

21.7 Adults Unable to Consent: N/A

- Permission: N/A
- Assent: N/A
- Dissent: N/A

## **23.0 Multi-Site Research**

Study-Wide Recruitment Methods:

Sites will draw on their clinical and community networks for recruitment, utilizing flyers and recruitment cards.

Study-Wide Recruitment Materials:

Recruitment flyers and cards will facilitate recruitment efforts.

Communication Among Sites:

Investigators, study coordinators, data managers, and data collectors from each site will have monthly or as needed calls to discuss matters of this study. Sites may contact other sites. Communication may be by phone, email, in person, fax, in person, or other forms of correspondence.

Communication to Sites:

Investigators, study coordinators, data managers, and data collectors from each site will have monthly or as needed calls to discuss matters of this consortium and this study. Sites may contact other sites. Communication may be in phone, email, in person, fax, in person, or other forms of correspondence.

## **24.0 Coordinating Center Research: N/A**

## **25.0 Resources Available**

Resources Available:

Overview of MN Regional SCIMS Resources. Located within the rich scientific milieu of Minnesota's "Medical Alley," our research program leverages world-class research infrastructure, core facilities, and one of the leading technology commercialization offices in the country. We will draw on this rich scientific environment to contribute to the national database, complete our proposed site-specific and module projects, and contribute to module projects proposed by collaborating Model System centers. UMN ranks ninth among public universities in research spending, with more than \$950 million in research expenditures in fiscal year 2019 and research awards of more than \$860 million. Blue Ridge ranked the UMN Department of Rehabilitation Medicine fifth nationally based on NIH funding in 2020. At Mayo Clinic, total research and education funding in 2018 exceeded \$1.1 billion. In 2018, Mayo Clinic's research programs generated 12,760 active IRB-approved studies: 3,067 new human research studies, 5,268 active grants and contracts, and 9,725 research and review articles in peer-reviewed journals.

